4.4.1.5.8 MAAE

A MAAE is a new onset or a worsening of a condition that prompts the participant to seek unplanned medical advice at a physician’s office or Emergency Department. Physician contact made over the phone or by e-mail will be considered a physician office visit for the purpose of MAAE collection. This includes medical advice seeking during the study visit or routine medical care. This definition excludes pediatric check-ups, follow-up visits of chronic conditions with an onset prior to entry in the study and solicited reactions.

MAAEs will be analyzed during the following time periods:

- Within 21 days after each injection
- During the study (ie, all MAAEs occurred during entire the study or the cutoff date which corresponds to the date of any interim analysis)

Note: MAAEs with date of onset before first vaccination (negative time of onset) will not be included in analysis but will be listed separately.

Main safety analysis will include only those MAAEs with time of onset before a participant received a non-study authorized/approved COVID-19 vaccine, if applicable. MAAEs with time of onset on or after the date of receiving a non-study authorized/approved COVID-19 vaccine will be listed separately.

4.4.2 Immunogenicity

The following derived endpoints are applicable to the neutralizing antibody titer against the SARS-CoV-2 D614G variant and other emergent variants, and the binding antibody titers to trimerized SARS-CoV-2 S protein.

4.4.2.1 Computed Values for Analysis

In order to appropriately manage extreme values (< lower limit of quantification [LLOQ] and > upper limit of quantification [ULOQ]) for analysis purposes, the following computational rule is applied to the values provided in the clinical database for each blood sample (BL) drawn:

- If a value is < LLOQ, then use the computed value LLOQ/2.
- If a value is between LLOQ and ULOQ, then use the value reported.
- If a value is > ULOQ, then use ULOQ

4.4.2.2 Fold-rise

The derived endpoint fold-rise is driven by both baseline and post-vaccination computed values as described in [Section 4.4.2.1](#) and is computed as individual titer ratio:

- Post-vaccination value divided by baseline value

Note: If baseline or post-baseline is missing, then fold-rise is missing.

4.4.2.3 Seroconversion

The seroconversion endpoint is driven by both baseline and post-baseline computed values as described in [Section 4.4.2.1](#) and a participant will have seroconverted if baseline values below LLOQ with detectable neutralization titer above assay LLOQ at D22, D36, D91 (Cohort 1) or D112 (Sentinel Cohort and Cohort 2), D181 (Cohort 1) or D202 (Sentinel Cohort and Cohort 2), and D366 (Cohort 1) or D387 (Sentinel Cohort and Cohort 2).

Note: If baseline or post-baseline is missing, then seroconversion is missing.

4.4.3 Additional Immunological Tests

4.4.3.1 T-Cell cytokine profile

A panel of soluble biomarkers in stimulated whole blood supernatants (TruCulture tubes) will be measured on D01, D22, and D36.

- Helper T cell type 1 (Th-1) and Helper T cell type 2 (Th-2) cytokines: Th1 cytokines include interferon-gamma (IFN γ), interleukin (IL)-2, and tumor necrosis factor alpha (TNF α); Th2 cytokines include IL-4, IL-5, IL-13.
- Additionally, pro-inflammatory cytokine IL-6, regulatory cytokine IL-10, Helper T cell type 17 (Th-17) cytokine IL-17, granulocyte-macrophage-colony-stimulating factor (GM-CSF), and IL-21 will also be measured.

The list of cytokines is subject to be updated based on more information and knowledge on SARS-CoV-2 before the enrollment of participants of Cohort 2.

All cytokines will be measured in whole blood following stimulation with full length S protein, SEB + anti-CD28 (positive control) and in unstimulated whole blood (negative control).

Computed values for analysis

For each participant and each cytokine listed above, 3 measurements will be available for analysis. The 3 measurements are positive control, negative control, and spike stimulant. Each cytokine has its own LLOQ and ULOQ. Similar as described in [Section 4.4.2.1](#), the computational rule below is applied.

- If a value is $< \text{LLOQ}$, then use the computed value $\text{LLOQ}/2$
- If a value is between $\geq \text{LLOQ}$ and $< \text{ULOQ}$, then use the value
- If a value is $\geq \text{ULOQ}$, then use the value of ULOQ

Two subtractions will be calculated as below for each cytokine with computed values described above:

- Subtraction 1: (spike stimulant – negative control)
- Subtraction 2: (positive control – negative control)

If the value of the above subtractions is $< \text{LLOQ}$, then the result will be reported as $\text{LLOQ}/2$

Fold-rise

To derive the fold-rise of cytokines, the ratio of post-vaccination and baseline values of the corresponding subtractions above are used. Therefore, there are 2 fold-rise values for each cytokine per participant per visit:

- Value of a post-baseline visit (spike stimulant – negative control) / baseline value of (spike stimulant – negative control)
- Value of a post-baseline visit (positive control – negative control) / baseline value of (positive control – negative control)

Note: If baseline or post-baseline computed value is missing, then fold-rise is missing.

Th-1/Th-2 ratios:

1. IFN γ /IL-4
2. IFN γ /IL5
3. IFN γ /IL-13
4. IL-2/IL-4
5. IL-2/IL-5
6. IL-2/IL-13
7. TNF α /IL-4
8. TNF α /IL-5
9. TNF α /IL-13

The ratios above are based on fold-rise. For each cytokine, there are 2 Th-1/Th-2 ratios, one for each subtraction above. The ratio based on subtraction of spike stimulant – negative control will be used as main supportive information for Th1/Th2 results. Among all ratios listed, IFN γ /IL-4 is the main Th-1/Th-2 ratio for characterizing Helper T cell polarization.

4.4.3.2 Memory B cells

Spike-Specific IgG and IgA Memory B cells will be quantified in peripheral blood mononuclear cells (PBMCs) at D01 (pre-vaccination) and at D112 (post-vaccination) using a fluorescent immunospot (FluoroSpot) assay. Both number of Spike-Specific IgG and IgA Memory B cells and number of total IgG and IgA Memory B cells are measured in Antibody Secreting Cells (ASC)/10⁶PBMCs. Proportion of Spike-Specific IgG and IgA Memory B cells in % will be calculated as follows: (number of Spike-Specific IgG and IgA Memory B cells ASC/10⁶PBMCs / number of total IgG and IgA Memory B cells ASC/10⁶PBMCs)* 100.

4.4.4 Efficacy

The efficacy endpoints are the virologically-confirmed COVID-19-like illness and serologic SARS-CoV-2 infection.

Virologically-confirmed COVID-19-like illness

Virologically-confirmed COVID-19-like illness is defined as a positive result for SARS-CoV-2 by Nucleic Acid Amplification Test (NAAT) on a respiratory sample in association with a COVID-19-like illness, which is defined in the protocol Section 8.2.2.1.

Serologically-confirmed SARS-CoV-2 infection

Serologically-confirmed SARS-CoV-2 infection is defined as a positive result in serum for the presence of antibodies specific to the nucleoprotein of SARS-CoV-2 detected by electrochemiluminescence immunoassay (ECLIA).

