**Table 1.6: Schedule of activities 4 (Follow-up of COVID-19-like illness)**

Contact Type	Initial Telephone Call*	Visit	Follow-up Telephone Call†
Verify information on COVID-19-like illnesses and schedule appointment for collection of respiratory samples as soon as possible after illness start date‡	X		
Collection of information on respiratory illness symptoms	X	X	X
Remind participant to complete Memory Aid or Diary Card	X	X	X
Collection of respiratory specimen		NPXXXX§	
Collection of disease burden and health care information	X	X	X
Collection of treatments received during COVID-19-like illness	X	X	X

\* Initial illness identification phone call. During the illness episode, participants may be contacted by the site staff for medical monitoring. The frequency of contact for medical monitoring is at the discretion of the investigator.

† Follow-up telephone call approximately 30 days after onset of illness

‡ Start of first clinical manifestation of COVID-19-like illness, unless during the first reactogenicity period (D01-D09) when the sample may be collected up to D09, at the Investigator's discretion.

§ "X" indicates that the nasopharyngeal swab number will be unique to each site. Further details are provided in the Operating Guidelines. A nasopharyngeal swab for central laboratory testing will be collected. A sample for local laboratory testing (clinical care) may be collected in addition to the NP swab for central laboratory testing. The swab will not be collected during a CLI visit if the date of collection is more than 14 days after resolution of symptoms.

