#### *COVID-19-Like Illness*

Symptoms of COVID-19-like illness are as listed below, along with an accompanying tabulation of terms used in the CRFs versus DCs/Memory Aids (Table 8.2).

New onset of any ONE of the following (that persists for a period of at least 24 hours or reoccurs within a 12-hour period):

- Cough (dry or productive)
- Fever (measured temperature > 100.4°F or > 38°C)
- Difficulty breathing or shortness of breath
- Anosmia
- Ageusia

- Chilblains (COVID-toes)
- Clinical or radiographic evidence of pneumonia
- Myocarditis, myocardial infarction
- Thromboembolic event (blood clots [eg, pulmonary embolism, deep vein thrombosis, stroke])
- Purpura fulminans

**OR**

New onset of any TWO of the following that are present at the same time (both symptoms that persist for a period of at least 24 hours or reoccurs within a 12-hour period):

- Pharyngitis
- Chills
- Myalgia
- Fatigue (malaise)
- Headache
- Rhinorrhea or nasal congestion
- Abdominal pain
- At least one of nausea or vomiting
- Diarrhea

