#### *Collection of Respiratory Samples*

For the duration of the study, the site will arrange for a respiratory sample to be taken if the participant experiences symptoms of COVID-19-like illness (see [Section 8.2.2.1](#)). After the onset of symptoms of COVID-19-like illness, the respiratory sample will be obtained as soon as

possible, unless during the first reactogenicity period (D01-D09) when the sample may be collected up to D09, at the Investigator's discretion.

All respiratory samples will be submitted for analysis by SARS-CoV-2 NAAT and a positive result will be considered a virologically-confirmed COVID-19-like illness (see [Section 8.2.2.4](#)). The samples (confirmed by SARS-CoV-2 NAAT) will be stored in a SP Sample Biorepository for further viral characterization, if needed.

If the respiratory sample swab cannot be collected, the research site will still collect the information mentioned below.

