**Table 10.3: Solicited systemic reactions: terminology, definitions, and intensity scales**

CRF term (MedDRA lowest level term [LLT])	Fever	Headache	Malaise	Myalgia	Arthralgia	Chills
Diary card term	Temperature	Headache	Feeling unwell or feeling tired	Muscle aches and pains	Joint pain	Chills
Definition	Elevation of temperature to $\geq 38.0^{\circ}\text{C}$ ( $\geq 100.4^{\circ}\text{F}$ )	Pain or discomfort in the head or scalp. Does not include migraine.	General ill feeling. Malaise is a generalized feeling of discomfort, illness, or lack of well-being that can be associated with a disease state. It can be accompanied by a sensation of exhaustion or inadequate energy to accomplish usual activities.	Muscle aches and pains are common and can involve more than one muscle at the same time. Muscle pain can also involve the soft tissues that surround muscles. These structures, which are often referred to as connective tissues, include ligaments, tendons, and fascia (thick bands of tendons).  Does not apply to muscle pain at the injection site which should be reported as injection site pain.	Pain in a joint or joints	Sensation of cold

CRF term (MedDRA lowest level term [LLT])	Fever	Headache	Malaise	Myalgia	Arthralgia	Chills
Intensity scale*	Grade 1: $\geq 38.0^{\circ}\text{C}$ to $\leq 38.4^{\circ}\text{C}$ , or $\geq 100.4^{\circ}\text{F}$ to $\leq 101.1^{\circ}\text{F}$	CRF: Grade 1: A type of adverse event that is usually transient and may require only minimal treatment or therapeutic intervention. The event does not generally interfere with usual activities of daily living.	CRF: Grade 1: A type of adverse event that is usually transient and may require only minimal treatment or therapeutic intervention. The event does not generally interfere with usual activities of daily living.	CRF: Grade 1: A type of adverse event that is usually transient and may require only minimal treatment or therapeutic intervention. The event does not generally interfere with usual activities of daily living.	CRF: Grade 1: A type of adverse event that is usually transient and may require only minimal treatment or therapeutic intervention. The event does not generally interfere with usual activities of daily living.	CRF: Grade 1: A type of adverse event that is usually transient and may require only minimal treatment or therapeutic intervention. The event does not generally interfere with usual activities of daily living.

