5.1.1.2 Statistical Methods for Primary Safety Objective

The following safety parameters will be used for the evaluation of safety. Additional parameters may be displayed as appropriate.

Solicited Reactions

Number and percentage of participants with:

- Presence of solicited injection site reactions and systemic reactions occurring up to 7 days after injection
- Each solicited reaction according to time of onset, maximum intensity, and number of days of occurrence over the solicited period

Unsolicited Events and Reactions

Number and percentage of participants with:

- Any unsolicited immediate systemic event in the 30 minutes after injection
- Any unsolicited event and reaction (using the current MedDRA version) 21 days after injection
- Any unsolicited event/reaction according to time of onset, maximum intensity, and duration

SAEs

Number and percentage of participants with:

- Any SAE within 21 days after injection and throughout the entire study according to SOC and PT, seriousness, and outcome

AESIs

Number and percentage of participants with:

- Any AESI within 21 days after injection and throughout the entire study according to SOC and PT, seriousness, and outcome

MAAEs

Number and percentage of participants with:

- Presence of MAAEs within 21 days after injection and throughout the entire study

Laboratory tests

- Presence of out-of-range biological test results up to 8 days post-last dose (ie, up to D09 for Cohort 1 and up to D30 for Sentinel Cohort and Cohort 2)
- Summary of toxicity grade shift from baseline

For descriptive purposes, the statistics presented in [Table 5.1](#) will be produced for the above safety parameters for each intervention group and each age group. The same dose-level group in Sentinel Cohort and Cohort 2 will also be pooled for analysis.

Harm analysis

Harm analysis assessed based on split of COVID-19 case will be assessed based on Safety Analysis Set (SafAS) at the time of the final analysis. Participants will be analyzed according to the study intervention they received. For the assessment, all dose-level arms will be pooled, and all placebo arms will be pooled as well.

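### Solicited vaccine reactions alone can satisfy the COVID-19-like-illness rule, and NAAT-positive episodes starting in the solicited window are not separated in the case counts (minor)

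*SAP*

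**What the plan says.** **Case definition.** SAP 4.4.4 and Protocol 8.2.2.1 both require a "positive result for SARS-CoV-2 by Nucleic Acid Amplification Test (NAAT) on a respiratory sample in association with a COVID-19-like illness". Neither sets aside any period after an injection.

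**Illness rule.** Protocol 8.2.2.1 has two routes. One sign is enough from a first list that includes "Fever (measured temperature > 100.4°F or > 38°C". Otherwise the rule is "New onset of any TWO of the following that are present at the same time", from a second list that includes chills, myalgia, fatigue (malaise) and headache. On the first route the sign must be one that "persists for a period of at least 24 hours or reoccurs within a 12-hour period"; the second route sets the same condition for both symptoms.

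**Solicited reactions.** Protocol Table 10.3 lists fever, headache, malaise, myalgia, arthralgia and chills, collected D01 to D08 after each injection (8.4.4). Appendix 10.3.1 treats all of them as vaccine-related by convention.

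**Swabbing.** In Protocol 8.2.2.2, symptoms of COVID-19-like illness trigger a respiratory sample. The next paragraph adds: "All respiratory samples will be submitted for analysis by SARS-CoV-2 NAAT and a positive result will be considered a virologically-confirmed COVID-19-like illness". The one provision that mentions reactogenicity concerns timing. The sample is taken as soon as possible, "unless during the first reactogenicity period (D01-D09) when the sample may be collected up to D09", at the Investigator's discretion (Table 1.6 and 8.2.2.2).

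**Use of the cases.** SAP 5.1.1.2 keeps one harm test for the final analysis: "Harm analysis assessed based on split of COVID-19 case will be assessed based on Safety Analysis Set (SafAS"), with dose levels pooled and placebo arms pooled. Case counts and percentages remain (SAP Table 5.1 and 5.2.5). SAP 5.1.3 keeps a summary of the last titer before infection among cases. Vaccine efficacy and correlates of risk are dropped (SAP 5.1.2.4).

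**The concern.** The same symptoms can be both a vaccine reaction and the illness half of a COVID-19 case. Take two participants, each with a silent infection at the time of injection. The vaccinee has headache and myalgia for a day and a half from D02, meets the rule, is swabbed and becomes a NAAT-confirmed case. The saline recipient has no symptoms, is not swabbed and does not become a NAAT case. Infection risk is equal, but the probability of being found is not.

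The error runs one way, toward more cases in vaccinees. Three retained outputs are exposed: the case percentages by arm, the vaccine/placebo split in the harm test, and the last titer before infection. On the last of these, an episode in the days after injection 1 has the D01 pre-vaccination sample as its last scheduled titer. The mFAS excludes participants positive at baseline in the pseudovirus assay, so that titer enters as LLOQ/2 (SAP 4.4.2.1). After injection 2 the last scheduled sample is the one drawn at D22 before that injection. With few cases, one or two such records could lower the vaccine group's summary.

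**Working it through.** **1. Overlap of terms.**

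| Table 10.3 solicited term | Illness rule, 8.2.2.1 |
|---|---|
| Fever, at or above 38.0°C | Yes, alone, if above 38°C |
| Headache | Yes, with one other |
| Malaise | Yes, as fatigue (malaise), with one other |
| Myalgia | Yes, with one other |
| Chills | Yes, with one other |
| Arthralgia | No |

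Five of six overlap. The participant-facing wording is also near identical for malaise, myalgia, headache and chills (Tables 8.2 and 10.3).

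**2. Safeguards in the text.** The D01-D09 provision may defer a swab after injection 1. It does not stop a positive from counting, and nothing equivalent exists for the window after injection 2.

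**3. Planned numbers (Protocol Table 1.2).** Vaccine 6 × 44 = 264, placebo 2 × 22 = 44, total 308, matching the stated target. Injections: vaccine 132 × 1 + 132 × 2 = 396; placebo 22 × 1 + 22 × 2 = 66. Null share of cases in vaccine: 264/308 = 0.857 (289/333 = 0.868 if the 25 Initial Sentinel participants are included).

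**4. Expected incidental cases** = injections × P(rule met after an injection) × P(incidental positive NAAT). The documents give neither probability. Assumed ranges: rule met after 30-70% of vaccine and 10-15% of placebo injections; incidental positivity 0.5-3%. Shift = vaccine cases − 0.857 × (vaccine + placebo cases).

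| Scenario (vaccine / placebo / positivity) | Vaccine | Placebo | Vaccine share | Shift |
|---|---|---|---|---|
| 30% / 15% / 0.5% | 0.59 | 0.05 | 0.92 | 0.04 |
| 50% / 15% / 1% | 1.98 | 0.10 | 0.95 | 0.20 |
| 70% / 10% / 3% | 8.32 | 0.20 | 0.98 | 1.02 |

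Middle row: 396 × 0.50 × 0.01 = 1.98; 66 × 0.15 × 0.01 = 0.10; 1.98 − 0.857 × 2.08 = 0.20. It adds 1.98/264 = 0.75 percentage points to the vaccine case percentage and 0.10/44 = 0.23 to placebo. Counting injection 2 only (132 and 22 injections), the middle row gives 0.66 and 0.03, a shift of 0.07. If the rule were met equally often in both arms, the share would stay at 0.857 and there would be no bias.

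**5. Harm test** (one-sided exact binomial, alpha 0.05, null 0.857). If every case is in vaccine, the p-value is 0.857^N: 0.053 at N = 19 and 0.046 at N = 20. Rejection is therefore impossible below 20 cases (22 if the null share is 0.868).

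False-signal probability with no true effect, averaging the exact test over a Poisson number of cases and counting both injections:

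| Genuine cases expected | No bias | 50% / 15% / 1% | 70% / 10% / 3% |
|---|---|---|---|
| 10 | 0.000 | 0.001 | 0.051 |
| 20 | 0.016 | 0.025 | 0.066 |
| 30 | 0.023 | 0.030 | 0.069 |

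For injection 2 only, with 20 genuine cases, the biased figures are 0.019 and 0.030.

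**The case against.** The strongest reply is that little is left for this to damage. Vaccine efficacy, correlates and the remaining interim analyses are cancelled. The harm test runs once, at the final analysis, and cannot reject with few cases. Enrollment and vaccination stopped in September 2021, so the planned injections are not the actual ones. An error toward apparent harm is also the cautious direction for a safety screen. All of this stands and limits the point to a minor one.

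It may also be said that nucleoprotein serology, scheduled at D01, D22 and D36, could find the silent placebo infection. That is true for the serological endpoint, and SAP 5.1.2.4 counts both endpoints as COVID-19 cases. It does not repair the NAAT endpoint, and the harm analysis does not say which endpoint it uses.

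A reader might infer more than the documents support:
- **That vaccinees are known to be swabbed more.** No reaction or swab rate is given. It is an inference from the saline placebo and the protocol's expectation that reactogenicity rises with dose (4.2).
- **That 8.2.2.2 makes any positive swab a case.** The preceding paragraph limits swabs to participants with illness symptoms and cites 8.2.2.1. The sentence is looser than the definition, but it does not replace it.
- **That a dose gradient distorts the harm test.** Doses are pooled there.
- **That counting from D01 is prescribed.** Neither document says so; they simply name no start. The separate tables, listings and figures document, which is not available here, may say more.

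**Conclusion.** The point holds as a minor one. The texts establish that solicited reactions alone can meet the illness rule, that a NAAT-positive episode in the solicited window then counts, and that the only allowance concerns swab timing after injection 1. The direction, toward excess vaccine cases, depends on vaccinees meeting the rule more often than saline recipients, which is likely but undocumented.

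The size rests on assumed rates and planned denominators: a shift of about 0.2 of a case in the middle scenario, with a range of 0.04 to 1.0. It would be tempting to conclude that the plan is set up to produce a false harm signal. The calculation does not support that: the false-signal rate stays within 0.05 except at the extreme of the assumed range. What is exposed is mainly descriptive: case counts and percentages, the harm split as displayed, and the pre-infection titer summary.

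**What to change.** In SAP 4.4.4, derive a flag for NAAT-positive episodes whose qualifying symptoms are only solicited systemic terms with onset D01 to D08 after either injection. Show the flagged episodes as a separate row by arm. Give the case percentages, the harm split and the pre-infection titer summary with and without them.

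In SAP 5.1.1.2, state which endpoint the harm analysis means by a COVID-19 case. State also that NAAT plus illness as defined in Protocol 8.2.2.1 governs over the looser sentence in 8.2.2.2. The sponsor should reconcile the first-period provision with the absence of any counterpart after injection 2; no swabbing rule is proposed here.

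The cost is SAP wording, one derived variable and a few table rows. Illness symptoms and duration (Protocol 8.2.2.2) and daily solicited records (SAP 4.4.1.1.1) are already collected. The downside is that some true early infections will fall in the flagged row, so both sets of counts must be shown and neither discarded.
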